5.9 STUDY DISCONTINUATION

Genentech, Study Center, and the Principal Investigator and the MD Anderson IND Office (as the IND Sponsor) have the right to terminate this study at any time. Reasons for terminating the study may include the following:

- The incidence or severity of AEs in this or other studies indicates a potential health hazard to patients
- Patient enrollment is unsatisfactory
- Data recording are inaccurate or incomplete
- Study protocol not followed

5.10 STATISTICAL METHODS

5.10.1 Analysis of the Conduct of the Study

This is a single-arm, Phase IIA, single-center, open-label study designed to evaluate the safety and efficacy of cobimetinib plus atezolizumab in approximately 20 patients per cohort of advanced rare cancers.

The efficacy analyses of OS, PFS, and ORR will be performed on all treated patients. DOR will be assessed in patients who have an objective response. The safety population will include all patients who received any amount of study drug. Patients who are enrolled into the study but do not receive any amount of study drug will not be included in the safety population.

5.10.2 Efficacy Analysis

5.10.2.1 **Primary Endpoint**

- ORR (PR or CR) per RECIST v1.1.

5.10.2.2 **Secondary Endpoints**

- Efficacy Endpoints:
 - a. ORR per irRECIST.
 - b. PFS per RECIST v1.1 and irRECIST.
 - c. OS
 - d. DCR and DOR per RECIST v1.1 and irRECIST.
- Safety Endpoints:
 - a. Adverse events per CTCAE v4.0.
- Translational Endpoints:
 - a. Tumor tissue and peripheral blood

5.10.3 Determination of Sample Size

The primary endpoint is best ORR (PR or CR), measured as per RECIST 1.1. Three parallel single-stage phase II trials will be conducted. A total of 60 patients will be enrolled, i.e., 20 patients in each tumor group. Considering the rareness of the disease, the patient accrual rate is approximately 1 to 2 patients per month per tumor group.

Sample size calculation

For each tumor group, we will estimate the best ORR and its exact confidence interval (CI). When the sample size is 20, and the response rate is 0.3, the two-sided 95% exact CI using the Clopper and Pearson method will be (0.119, 0.543).

For each tumor group, we will also compare its overall best response rate to the historical control based on the current literature. Let p represent the overall best response rate, we will perform independent Binomial test against $H_0: p=0.1$ for each group, with a 1-sided type I error rate of 0.05. The sample size of 20 will provide 76% power to detect an improved best ORR being 30% compared to 10%.

Analysis Plan

The primary outcome is the best ORR since the start of treatment. For each tumor group, we will estimate the best response rate and its 95% exact confidence interval using the Clopper and Pearson method. And we will assess the efficacy of the combination treatment by performing the independent binomial test comparing the best response rate versus the historical control for each tumor group. The primary efficacy analyses will include all treated patients who have received at least one dose of study treatment and have baseline tumor assessment. Patients who do not receive at least 1 dose of therapy will be replaced.

For each tumor group, median DOR and corresponding 2-sided 95% CI will be reported. The association between the best ORR and other variables will be assessed using the Fisher's exact test. Time-to-event outcomes, including progression free survival (PFS) and overall survival (OS), will be estimated using Kaplan-Meier method. The log-rank test will be performed to test the difference in time-to-event distributions between patient groups. Cox proportional hazards model may be utilized to include multiple covariates in the time-to-event analysis.

Patients' demographic information (e.g. age, gender) at baseline will be analyzed, with data summarized in mean \pm standard deviation, median and range for continuous variables, and in frequency count and percentage for categorical variables. The student t-test or the Wilcoxon test may be used to compare continuous variables among different tumor patient groups. The chi-square test or the Fisher's exact test will be applied to assess the association between two categorical variables.

The safety analyses will include all treated patients who received at least one dose of study treatment. Toxicity data will be summarized by frequency tables for each tumor type group. The association between the types and severity of toxicity and the tumor group will be evaluated. No formal statistical testing will be performed on these summaries.

Summary statistics for biomarkers and their corresponding changes (or percent changes) from baseline will be tabulated by planned study day and dose in each tumor group. The time-course of biomarker measures will be investigated graphically. If there is indication of meaningful pattern over time, further analysis (eg, by linear mixed model) may be performed to characterize the relationship. Methods such as, but not limited to, logistic regression will be used to explore possible associations between biomarker measures and clinical outcomes.

MDACC Investigational New Drug (IND) office will review safety/efficacy data with Principal Investigator (and statistician if needed) at a predetermined interval as indicated next. The first analysis will occur after the first 5 subjects are treated for at least 2 cycles, per tumor group. Reports submission will continue in cohort size of 5, per tumor group, thereafter. On every report submission, the information from previous reported patients will need to be updated.

Considering the limited sample size for each tumor group, we may apply the Bayesian classification and information sharing method proposed by Lee and Chen (submitted) in the data analysis. It will provide a more efficient and more powerful way to estimate and test the response

rate for similarly performed groups. We will first cluster the tumor groups according to their response rate into the low- or high-response cluster first, and then apply the Bayesian hierarchical model to borrow information among groups within the same cluster in estimating their response rate and comparing it to the historical control.

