4. STUDY DESIGN

4.1 DESCRIPTION OF THE STUDY

This study will be a single-arm, open-label, non-randomized trial evaluating the combination of cobimetinib, a highly selective, oral, reversible inhibitor of MEK1 and MEK2, and atezolizumab, a fully humanized monoclonal programmed cell death ligand 1 (PD-L1) antibody, in multiple cohorts of patients with advanced rare tumors. After signing informed consent, all eligible patients will be treated with a combination of cobimetinib and atezolizumab (See Study schema). The primary objective is to assess the efficacy of this combination as measured by ORR using RECIST v1.1.

[figure not shown]
Tumor response will be evaluated according to RECIST v1.1 (see Appendix 6). Any evaluable and measurable disease must be documented at screening and re-assessed at each subsequent tumor evaluation. Investigators will assess tumor response at 8 week intervals, regardless of any dose delays or treatment cycle. Treatment beyond initial investigator-assessed RECIST 1.1-defined progression will be considered in subjects experiencing investigator-assessed clinical benefit and tolerating study therapy (especially during the flare time-window of the first 12 weeks of treatment to account for expected delayed response). In such cases confirmation of progression is recommended minimum 4 weeks after the first immune-related PD assessment. Such subjects must discontinue therapy when further progression is documented.

All patients will be closely monitored for safety and tolerability during all cycles of therapy, at the treatment discontinuation visit, and during the follow-up period. The NCI CTCAE v4.0 will be used to characterize the toxicity profile of the study treatments on all patients.

After discontinuation of study treatment, patients may receive any subsequent line therapy as directed by their treating physician.

Patients who discontinue treatment for reasons other than disease progression (e.g., toxicity) will continue scheduled tumor assessments until disease progression, withdrawal of consent, study termination by Sponsor, or death, whichever occurs first. In the absence of disease progression, tumor assessments should continue regardless of whether patients start a new anti-cancer therapy, unless consent is withdrawn. All patients will be followed for survival unless consent is withdrawn.

Figure 1: Study Schema

[figure not shown]

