5.4.1 Permitted Therapy

The following therapies are permitted in the study:

- Hormonal therapy with gonadotropin-releasing hormone agonists or antagonists for prostate cancer
- Oral contraceptives
- Hormone-replacement therapy
- Prophylactic or therapeutic anticoagulation therapy (such as low-molecular weight heparin or warfarin at a stable dose level)
- Palliative radiotherapy (e.g., treatment of known bone metastases) provided it does not interfere with assessment of tumor target lesions. It is not required to withhold avelozumab during palliative radiotherapy.
- Surgery (preferable) or definitive radiation therapy (with or without radiosensitizing agent) for patients specifically enrolled in the cutaneous squamous cell carcinoma cohort when upfront surgery was considered functionally or cosmetically inappropriate is allowed after a minimum of two cycles of therapy with the investigational agents.
- Inactive influenza vaccinations during influenza season ONLY
- Megestrol administered as an appetite stimulant
- Inhaled corticosteroids for chronic obstructive pulmonary disease
- Mineralocorticoids (e.g., fludrocortisone)

Anti-emetics and anti-diarrheal medications should not be administered prophylactically before initial treatment with study drugs. At the discretion of the investigator, prophylactic anti-emetic and anti-diarrheal medication(s) may be used per standard clinical practice before subsequent doses of study drugs. Hematopoietic growth factors should not be administered prophylactically before initial treatment with study drugs. Hematopoietic growth factors may be administered according to local guidelines if indicated during the course of the study.

In general, investigators should manage a patient's care with supportive therapies as clinically indicated, as per local standards. Patients who experience infusion-associated symptoms may be treated symptomatically with acetaminophen, ibuprofen, diphenhydramine, and/or famotidine or another H2 receptor antagonist as per standard practice (for sites outside the United States, equivalent medications may be substituted per local practice). Serious infusion-associated events manifested by dyspnea, hypotension, wheezing, bronchospasm, tachycardia, reduced oxygen saturation, or respiratory distress should be managed with supportive therapies as clinically indicated (e.g., supplemental oxygen and b2-adrenergic agonists).

All medications must be recorded on the Concomitant Medications eCRF.

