5.4.2 Therapy Not Permitted

Any concomitant therapy intended for the treatment of cancer, whether health authority-approved or experimental, is prohibited for various time periods prior to starting study treatment, depending on the anti-cancer agent, and during study treatment until disease progression is documented and patient has discontinued study treatment. This includes but is not limited to chemotherapy, hormonal therapy, immunotherapy, radiotherapy, investigational agents, or herbal therapy.

The following medications are prohibited while receiving study treatment, unless otherwise noted:

- Traditional herbal medicines as their use may result in unanticipated drug-drug interactions that may cause or confound assessment of toxicity.
- Any live, attenuated vaccine (e.g., FluMist®) within 4 weeks prior to treatment start date or at any time during the study or within 90 days following the last infusion of atezolizumab.
- For patients on atezolizumab:
 - Use of steroids to premedicate patients for whom CT scans with contrast are contraindicated (i.e., patients with contrast allergy or impaired renal clearance); in such patients, MRIs of the chest, abdomen, and pelvis with a non-contrast CT scan of the chest must be performed.
 - Immunomodulatory agents, including but not limited to interferons or IL-2, during the entire study; these agents could potentially increase the risk for autoimmune conditions when received in combination with atezolizumab
 - Immunosuppressive medications, including but not limited to cyclophosphamide, azathioprine, methotrexate, and thalidomide; these agents could potentially alter the activity and the safety of atezolizumab
 - Systemic corticosteroids and TNF- α inhibitors may attenuate potential beneficial immunologic effects of treatment with atezolizumab. Therefore, in situations where systemic corticosteroids or TNF- α inhibitors would be routinely administered, alternatives, including antihistamines, should be considered first by the treating physician. If the alternatives are not feasible, systemic corticosteroids and TNF- α inhibitors may be administered at the discretion of the treating (see Section 4.4.2)
- For patients on cobimetinib:

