5.6.5 Tumor and Response Evaluations

Patients will undergo tumor assessments at baseline and every 8 weeks in all cohorts assessed, regardless of dose delays, until radiographic disease progression per RECIST v1.1 or (for atezolizumab treated patients who continue treatment after radiographic disease progression) loss of clinical benefit as determined by the investigator. Thus, tumor assessments are to continue according to schedule in patients who discontinue treatment for reasons other than disease progression or loss of clinical benefit, even if they start new anti-cancer therapy. At the investigator's discretion, tumor assessments may be repeated at any time if progressive disease is suspected.

All measurable and evaluable lesions should be assessed and documented at screening. Tumor assessments performed as standard of care prior to obtaining informed consent and within 28 days prior to initiation of study treatment do not have to be repeated at screening.

Cross sectional imaging will be performed with either contrast enhanced CT or MRI. RECIST 1.1 criteria will be used to determine disease response.

If a CT scan for tumor assessment is performed in a positron emission tomography (PET)/CT scanner, the CT acquisition must be consistent with the standards for a full contrast diagnostic CT scan.

All measurable and evaluable lesions should be re assessed at each subsequent tumor evaluation. The same radiographic procedures used to assess disease sites at screening should be used for subsequent tumor assessments (e.g., the same contrast protocol for CT scans).

Response will be assessed by a blinded radiologist at the MD Anderson Quantitative Imaging Analysis Core using RECIST v1.1 (see Appendix 2) and immune-modified RECIST (see Appendix 5). Assessments should be performed by the same evaluator, if possible, to ensure internal consistency across visits. Results must be reviewed by the investigator before dosing at the next cycle.

For cutaneous squamous cell carcinoma, since “surgery (preferable) or definitive radiation therapy (with or without radiosensitizing agent)” is allowed for patients after initial response, such a definitive local therapy can only be performed after at least 1 tumor assessment.

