5.6.8 Follow-Up Assessments

Please see Appendix 1 for the schedule of assessments performed during the study.

- **For progression-free survival follow-up**

Patients who discontinue treatment for reasons other than disease progression (e.g., toxicity) will continue scheduled tumor assessments until disease progression, withdrawal of consent, study termination by PI, or death, whichever occurs first.

- **For survival follow-up**

Patients who discontinue study treatment for reasons other than withdrawal of consent will be followed for survival and subsequent anti-cancer therapies approximately every 3 months until death, loss to follow-up, withdrawal of consent, or study termination by PI. During this period, documentation of anti-cancer therapies should include administration start and stop dates.

Required follow-up information will be collected via telephone calls and/or clinic visits every 3 months until death, withdrawal of consent, the patient is lost to follow-up, or study termination by the Sponsor, whichever occurs first.

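### The primary best ORR has no cut-off at non-study anti-cancer therapy, so a PR first reached after cSCC surgery, definitive radiation or a later therapy could be counted as a response to the combination

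*Combined protocol and SAP*

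**What the plan says.** The Analysis Plan in section 5.10.3 defines the endpoint this way: "The primary outcome is the best ORR since the start of treatment". The analysis set is every treated patient with a baseline tumor assessment. There is no rule for patients who receive other anti-cancer therapy, and sections 4.4.1, 5.10.1 and 5.10.2 add none.

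Other sections bear on which scans could feed that endpoint:

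- Section 4.1 allows further lines of therapy once study treatment stops, and adds: "In the absence of disease progression, tumor assessments should continue regardless of whether patients start a new anti-cancer therapy". Section 5.6.5 likewise continues scheduled scans in patients who stop for reasons other than progression or loss of clinical benefit, "even if they start new anti-cancer therapy".
- Section 5.4.1 permits surgery or definitive radiation for cSCC patients in whom upfront surgery was judged inappropriate on functional or cosmetic grounds. It "is allowed after a minimum of two cycles of therapy with the investigational agents". Palliative radiotherapy in the same list is allowed only "provided it does not interfere with assessment of tumor target lesions"; the cSCC item has no such proviso.
- Section 5.6.5 says of cSCC local therapy that it "is allowed for patients after initial response, such a definitive local therapy can only be performed after at least 1 tumor assessment".
- Section 5.4.2 bars other cancer therapy "during study treatment until disease progression is documented and patient has discontinued study treatment".
- Section 5.6.8 lists scans after early discontinuation under the label "For progression-free survival follow-up".
- Appendix 2 defines PR as a fall of at least 30% from baseline in the target-lesion sum, with no condition that the patient is still on study therapy. CR must persist for two or more cycles of therapy.

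**The concern.** The primary ORR is meant to measure the activity of cobimetinib plus atezolizumab against a 10% historical rate. The plan opens the response window at first dose, never closes it, and continues scanning after other treatment has begun. A patient with stable disease who then has a target lesion removed or irradiated, or who stops study treatment and starts another drug, could later show a 30% fall from baseline. On the plan's wording that is a PR, and it counts.

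The error runs one way, since a misattributed PR can only add to the numerator. In cohorts of 20, one extra responder can decide whether the null is rejected. Without a written rule, such patients would have to be classified once their outcomes are known, in an open-label trial whose optional interim efficacy analyses are run and interpreted by the study team (section 5.10.4).

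**Working it through.** **Inputs.** Section 5.10.3: n = 20 per cohort, null ORR 10%, one-sided 0.05, alternative 30%, power 76%. Section 5.3: 28-day cycles. Section 5.6.5: scans every 8 weeks. The number of exposed patients and their chance of a later PR are not in the documents and are assumed below.

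**1. The plan's own figures.** P(Bin(20, 0.10) ≥ 4) = 0.1330 and P(Bin(20, 0.10) ≥ 5) = 0.0432, so the test rejects at 5 or more responders. Power is P(Bin(20, 0.30) ≥ 5) = 0.7625, matching 76%. The Clopper-Pearson interval for 6/20 is (0.119, 0.543), as stated.

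**2. Timing in cSCC.** Two cycles are 2 × 28 = 56 days, or 8 weeks. Local therapy therefore becomes available when only one scheduled post-baseline scan need have been done.

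**3. Effect of one patient.**

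- 4/20: p = 0.133, 95% CI 5.7% to 43.7%; not rejected.
- 5/20: p = 0.043, 95% CI 8.7% to 49.1%; rejected.

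The chance that a cohort has exactly 4 drug responders, one short of rejection, is 0.1330 − 0.0432 = 0.0898 at a true ORR of 10%. At a true ORR of 20% it is C(20,4) × 0.2⁴ × 0.8¹⁶ = 0.2182.

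**4. False-positive rate at a true ORR of 10%.** Let k patients be exposed to other therapy, and let c be the chance that an exposed drug non-responder is then scored PR. An exposed patient counts as a responder with probability π = 0.10 + 0.90c. The count is Bin(20−k, 0.10) + Bin(k, π), and the test rejects at 5 or more.

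- k = 1: P(Bin(19, 0.10) ≥ 5) + π × P(Bin(19, 0.10) = 4) = 0.0352 + π × (0.1150 − 0.0352) = 0.0352 + 0.0798π.
- k = 2: 0.0282 + 0.0700 × [1 − (1−π)²] + 0.1680 × π². The constants are P(≥ 5), P(= 4) and P(= 3) for Bin(18, 0.10).

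| c | π | k = 1 | k = 2 |
|---|---|---|---|
| 0 (no later PR) | 0.10 | 4.3% | 4.3% |
| 0.1 | 0.19 | 5.0% | 5.8% |
| 0.3 | 0.37 | 6.5% | 9.3% |
| 0.5 | 0.55 | 7.9% | 13.5% |
| 1 (ceiling) | 1.00 | 11.5% | 26.6% |

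The last row applies only if one or two misattributed PRs are certain.

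**The case against.** The best defence is that the exposure is narrow.

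- **cSCC route.** Section 5.4.1 confines local therapy to patients unsuited to upfront surgery. Section 5.6.5 describes it as following an initial response. If that is a condition, those patients are already responders and cannot be converted. However, 5.4.1 asks only for two cycles, and the explicit limit in 5.6.5 is one tumor assessment, so the sections do not settle the matter.
- **Later-therapy route.** This is the only route in the appendiceal and small bowel cohorts. Section 5.4.2 joins progression and discontinuation before other therapy is released, so a literal reading holds back a non-progressing patient. Section 4.1 nevertheless expects patients without progression to start new therapy and continue scans. Section 5.4.2 governs conduct; it does not say how a response is scored.
- **Intent.** Appendix 2 presents the criteria as measuring response to treatment, 5.10.3 says the test assesses the combination, and 5.6.8 ties later scans to PFS. These point away from counting such a PR but do not exclude it. The blinded radiologist who reads response under 5.6.5 is given no instruction on local therapy.
- **Measurability.** Appendix 4 leans towards treating previously irradiated or locally treated lesions as not measurable, and partly measured cases as not evaluable. Both statements are qualified as the usual course, sit in the immune-modified criteria, and do not directly address target lesions treated on study.
- **Size.** The exposure figures are assumed, and any single misclassified patient matters at n = 20. Section 5.10.4 calls the study hypothesis-generating.

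What stands is that the exposure is probably small and its size cannot be derived from the documents. That no cut-off exists is not in dispute.

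**Conclusion.** The concern holds. The primary endpoint lacks an end to its response window, and the protocol itself generates scans after other therapy, so the stated rules would count a PR first reached after that therapy. CR is less exposed because Appendix 2 requires it to last at least two cycles of therapy.

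The direction of bias is certain; its size is not. The table's 10% to 50% range assumes one or two exposed patients in a cohort and should be read as illustration. Exposure is likely to be low, and lower still in cSCC if an initial response is a binding condition for local therapy. The plan's sample size, rejection rule and power are correct and unaffected. The definition should be settled before analysis because one patient can change a cohort's conclusion and the remedy is cheap.

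**What to change.** In the Analysis Plan of section 5.10.3, state that best response for the primary ORR uses RECIST v1.1 assessments from first dose up to the first non-study anti-cancer therapy, including cSCC surgery or definitive radiation. Patients with a PR or CR before that point remain responders. Patients with none stay in the denominator as non-responders. Palliative radiotherapy that meets the section 5.4.1 proviso on target lesions need not trigger the cut-off.

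Sections 5.4.1 and 5.6.5 must be reconciled on whether cSCC local therapy follows a response. Whether the RECIST v1.1 window also closes at progression for patients treated beyond it is a separate definition for the sponsor to state.

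The cost is a wording change and one reconciliation, with no new visits and no change to n = 20, the threshold of 5 or the power. Section 5.6.8 already records start and stop dates of subsequent anti-cancer therapy; the sponsor should confirm that cSCC surgery and radiation dates are captured in the same way. The downside is a possibly slightly lower observed ORR: a patient whose tumor is shrinking but is short of 30% at the week 8 scan, and who then has local therapy, is scored a non-responder although the protocol expects some delayed responses. That is a conventional, conservative choice.

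### Section 5.10.3 allows an optional Bayesian borrowing test of the same response rate without stating its precedence, its settings or its error rate

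*Combined protocol and SAP*

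**What the plan says.** Section 5.10.3 sets out the design as follows: "Three parallel single-stage phase II trials will be conducted". On size: "A total of 60 patients will be enrolled, i.e., 20 patients in each tumor group". For the comparison with the historical control: "we will perform independent Binomial test against $H_0: p=0.1$ for each group", "with a 1-sided type I error rate of 0.05". The stated power is 76% at a true rate of 30%. The Analysis Plan in the same section, having named best ORR as the primary outcome, commits to that test: "we will assess the efficacy of the combination treatment by performing the independent binomial test".

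The closing paragraph of the section adds an option: "we may apply the Bayesian classification and information sharing method". It is presented as more efficient and more powerful, for testing as well as estimation. The procedure begins: "We will first cluster the tumor groups according to their response rate into the low- or high-response cluster". A hierarchical model then borrows among the cohorts in a cluster, both to estimate their response rates and to compare them with the historical control. The source is a submitted manuscript that has no entry in the reference list (Section 10).

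The section does not say when the option would be used, how the clusters are cut, what the prior is, or what posterior probability counts as success. It also does not say how a Bayesian result ranks against the binomial result. By contrast, Section 5.10.5 gives the Bayesian toxicity rule a posterior threshold, stopping boundaries and simulated operating characteristics.

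**The concern.** The binomial test and the Bayesian method address the same endpoint against the same historical control. The second method groups cohorts by the outcome under test, and its use and settings are left open. The trial is open-label. Section 5.10.3 has safety and efficacy data reviewed with the principal investigator after every 5 patients per cohort, and Section 5.10.4 allows up to two interim efficacy analyses interpreted by the study team. The decision to borrow, and how strongly, could therefore be taken with responses already known.

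At stake is the meaning of a positive cohort. A cohort with 3 or 4 responses in 20 fails the binomial test, but could be reported as beating the historical control because its cluster-mates responded. A reader would then attach the stated 5% error to a result that does not carry it.

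**Working it through.** **Inputs from Section 5.10.3.** n = 20 per cohort, three cohorts, null rate 0.10, alternative 0.30, one-sided 0.05.

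**Step 1: the plan's own figures.** With X ~ Binomial(20, p):
- Pr(X ≥ 4 | 0.10) = 0.1330, above 0.05.
- Pr(X ≥ 5 | 0.10) = 0.0432, so the rule is 5 or more.
- Pr(X ≥ 5 | 0.30) = 0.7625, matching the stated 76%.
- The Clopper-Pearson interval for 6/20 is (0.119, 0.543), as stated.

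**Step 2: how borrowing changes a result.** The plan gives no settings, so these are assumptions. Let m be the mean observed rate of the other cohorts in the same cluster. Give the cohort a Beta(wm, w(1−m)) prior, where w is the prior's worth in patients. With x responses the posterior is Beta(wm + x, w(1−m) + 20 − x). Call it a success if Pr(p > 0.1) > 0.95. A cohort with no cluster-mate gets a vague prior.

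Example: x = 4, m = 0.30, w = 10. The posterior is Beta(7, 23) and Pr(p > 0.1) = 0.978, a success. The exact binomial p-value for 4/20 is 0.133, a failure.

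**Step 3: error of a cohort truly at 10%.** All outcomes of the three cohorts were enumerated exactly. The cohort counts as positive if either method succeeds. Entries are for w = 5 / 10 / 20.

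| Meaning of a high-response cohort | Other two at 30% | All three at 10% |
|---|---|---|
| 3/20 or more (at or above 15%) | 9.9% / 21.1% / 29.1% | 4.5% / 5.0% / 7.4% |
| 4/20 or more (at or above 20%, or strictly above 15%) | 10.3% / 12.8% / 13.2% | 4.5% / 5.1% / 6.5% |
| 5/20 or more (strictly above 20%) | 4.3% / 4.3% / 6.3% | 4.3% / 4.3% / 4.5% |

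Using the Bayesian test alone, with the vague prior for an isolated cohort, gives the same figures.

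**Step 4: hand check of two cells.** Take the second row at w = 20. A cohort at 4/20 passes whenever at least one other cohort is also at 4/20 or more. Pr(X = 4 | 0.10) = 0.1330 − 0.0432 = 0.0898.
- Others at 30%: Pr(X < 4 | 0.30) = 0.1071, so the error is 0.0432 + 0.0898 × (1 − 0.1071²) = 0.132.
- All at 10%: Pr(X < 4 | 0.10) = 0.8670, so the error is 0.0432 + 0.0898 × (1 − 0.8670²) = 0.065.

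**Step 5: sensitivity to the assumed model.** A hierarchical normal model on the logit scale, with cuts at 3/20 or 4/20 and the same 0.95 threshold, gave 12.6% to 30.4% with both other cohorts at 30%, and 4.7% to 7.1% with all at 10%. In the beta model, raising the threshold to 0.975 with w = 5 brings the mixed-scenario error to about 5% or less. The answer depends on exactly the settings that the protocol leaves out.

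**The case against.** The strongest reply is that the plan does say which test assesses efficacy. The binomial test is committed to in firm terms, directly after the primary outcome is named, and the null, error rate, sample size and power all belong to it. The synopsis describes no other efficacy test. The Bayesian method is optional, comes at the end of the section and is never called primary. Section 5.10.4 describes the study as hypothesis-generating, and borrowing across small cohorts is a recognised reason for such a model.

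Most of this stands, and it rules out three stronger readings that a reader might infer:
- That the plan declares a second primary test. It does not. What is missing is a statement of precedence and a supportive label.
- That the binomial test loses its 5% error. It does not: its exact error stays at 4.3% whatever else is run. Inflation arises only if the Bayesian method may also, or instead, declare a cohort positive.
- That the method has no calibration. The submitted manuscript may contain one. The documents support only that the protocol states no settings and no error rate.

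The reply does not remove the gap. The optional paragraph speaks of testing and of comparison with the historical control, so it cannot be read as estimation only. A hypothesis-generating label does not settle what a stated 5% error refers to.

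**Conclusion.** The point holds as one of missing precedence and missing specification. The documents establish that an optional, outcome-clustered test of the same rate against the same control sits beside the named binomial test, with no rank, settings or error rate given.

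The size cannot be derived from the documents. Under the assumed beta model with a 0.95 threshold and the other two cohorts at 30%, the error for a 10% cohort runs from 4.3% (no inflation) to 29.1%. The cluster cut and its tie rule matter as much as the prior weight, because 3/20 and 4/20 fall exactly on cuts of 15% and 20%. With all three cohorts at 10% the range is 4.3% to 7.4%, so the problem is material mainly when other cohorts truly respond. The stated sample size and power need no correction.

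**What to change.** In Section 5.10.3, state that the per-cohort exact binomial test (5 or more responses in 20) alone determines whether a cohort is declared positive. State also that the Bayesian clustering and borrowing model is supportive estimation only, reported alongside it.

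The cost is one sentence of amendment. The stated error and power are unchanged. What is given up is that borrowing can no longer turn a negative cohort positive.

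If the sponsor does want the model to test, the cluster rule (including ties), prior and posterior threshold should be fixed before any efficacy review. The simulated per-cohort error should then be reported with all cohorts at 10% and with one or both of the others at 30%. That costs a short simulation.
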